15.1. Device Deficiency

A Device Deficiency (DD) is an inadequacy of a medical device with respect to its identity, quality, durability, reliability, usability, safety or performance.

Note 1: Device deficiencies includes malfunctions, use errors and inadequacy in the information supplied by the manufacturer including labelling.

Note 2: This definition includes device deficiencies related to the investigational medical device (3.29) or the comparator

15.2. Reporting Procedures

AE of any kind and DD will be recorded in the applicable CRF and source notes. The collection of AE's is started at the time of the procedure.

The Investigator will evaluate all AE for seriousness, severity and relationship to the device and procedure. The following reporting timelines should be followed for the AE/DD information to be submitted/entered into the CRF and reported to the Sponsor or designee:

- ADE and DD – will be reported in a timely manner (within 3 working days of the investigator being informed about the event)
- SAE, SADE and DD with potential to cause SADE – immediately (i.e. within 24 hours of the investigator being informed about the event)

To report: Enter data into the EDC system. This will generate an automated email to the clinical team. If you do not have access to the EDC system, call Access Vascular at [REDACTED] and/or email the clinical team at [REDACTED]

For ADE, SADE and DD, details of the product/procedure related to the event will be included and where applicable, pictures taken of the device. The deficient product should be retained for return to the sponsor via the return kits. Depending on the nature of the adverse event, the sponsor may request copies of the subject's medical records, Imaging, Operative notes, as well as results of any relevant laboratory tests performed or other documentation related to the AE. If the subject was hospitalized, a copy of the discharge summary may be requested by the sponsor and should be forwarded as soon as it becomes available. A narrative of these ADE, SADE, or DD may be required to provide a summary of the event.

The Investigator and investigative site will also be responsible for required reporting to the site's Institutional Review Board / Independent Ethics Committee (IRB/IEC) for all AEs, SAEs, and UADEs.

Ongoing Adverse Events at Study Discontinuation

At the time of data analysis (e.g., interim or final), an evaluation of ongoing events should take place and be listed as ongoing in the safety table.

16. Statistical Design

16.1. General Considerations

Study data will be made available in listings or electronic files as needed. The study results will be reported in tabular form using descriptive statistics, confidence intervals, or statistical tests as indicated.

All summaries will be done by randomized treatment group. Numeric descriptive statistics include the n, mean, standard deviation (SD), median, minimum value, and maximum value. These will be calculated for all numeric baseline data. Categorical summaries will show the number and percent of subjects in the levels associated with the variable summarized and the analysis performed. Percentages will be calculated based on the total number of subjects with non-missing data for the assessment. The denominator should be included for each summary to indicate the set of subjects being summarized.

For any inferential analyses, a two-sided p-value of less than or equal to 0.05 will be considered statistically significant. Any confidence intervals provided will be two-sided 95% intervals. The primary effectiveness assessment is considered the primary analysis. This study is not intended to support claims and the other statistical tests included are intended to assist with reporting, hence, no other adjustment for multiplicity will be used.

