10.7. Enrollment

A subject is considered enrolled when the assigned PICC is inserted. Due to the current situation with COVID, the sponsor is concerned about lost to follow up rates. To prepare for this, the site will enroll 4 extra subjects bringing the total to 24. The plan is to analyze 10 enrolled subjects on each arm, but the site will recruit for 12 in case of COVID related follow up issues.

Screening process

A Prospective, Randomized PICC Asymptomatic Thrombosis Study (PROPATH)	Number: 20-002 Version: C 28Apr2021 Page: 17 of 30
---	---

11. Discontinued Subjects

If a subject is unable to complete the study for any reason, then the investigator will use the screen failed randomization envelope to recruit for this discontinued subject. Data from the discontinued subject will not be used for the per protocol analysis. However, demographics will be used for the recruitment analysis. Any subjects in section 12 described below will be replaced using the method mentioned in this paragraph.

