16.3. Analysis Populations

The primary analysis will be based on a Full Analysis Set (FAS) analysis population defined as those who were randomized and met all inclusion and exclusion criteria. A Per-Protocol (PP) population will be completed that excludes subjects who have one or more major protocol deviations. Major protocol deviations will be identified prior to locking the database for the final analysis and will include, but are not limited to, not receiving the randomized treatment, not completing the study, and not have met all inclusion and exclusion criteria. Information for subjects not in the FAS population will be listed if available.

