16.5.3. Analysis of Other Endpoint(s)

Failure and safety endpoints will also be compared between the HydroPICC group and control group using Fisher's exact tests.

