16.6. Adverse Event Analyses

A listing of all individual AEs will be provided. Summary tables will be presented by system organ class based on the Medical Dictionary for Regulatory Activities (MedDRA Version 18.0 or higher) terminology list (preferred terms). The number and percentage of subjects with one or more event will be summarized by treatment group along with the total number of events. This summary will be provided for all AEs, SAEs, device-related AEs, and device-related SAEs.

All SAEs will also have a detailed narrative provided.

17. Data Management

The data collected in the CRFs will be entered into a database. The data will be subject to verification, validation and archiving according to the standard operating procedures of the Sponsor. The data will be analysed with reference to the analysis plan. Any deviations from the planned analysis will be documented in the final study report.

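### Adverse events are tabulated by randomized arm with no safety population or device-received rule, so an event can be counted against a device the subject never had

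*Combined protocol and SAP*

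**What the plan says.** All references are to the combined protocol and SAP.

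- **Grouping.** Section 16.1 states, without exception: "All summaries will be done by randomized treatment group".
- **Populations.** Section 16.3 defines two sets. For the first: "The primary analysis will be based on a Full Analysis Set (FAS) analysis population defined as those who were randomized and met all inclusion and" (the sentence then adds the criteria for exclusion). The second, the per-protocol set, removes subjects with major deviations, and the examples given are "not receiving the randomized treatment, not completing the study, and not have met all inclusion and exclusion criteria". For everyone else: "Information for subjects not in the FAS population will be listed if available". There is no safety or as-treated set.
- **Adverse events.** Section 16.6 covers all AEs, SAEs, device-related AEs and device-related SAEs: "The number and percentage of subjects with one or more event will be summarized by treatment group along with the total number of events". It names no population and no rule based on the device received. It also promises a listing of every AE and a narrative for every SAE.
- **Failure and safety endpoints.** Section 16.5.3 says: "Failure and safety endpoints will also be compared between the HydroPICC group and control group", by Fisher's exact test. Again no population is named.
- **Screen failures.** Section 10.6 treats any consented subject who does not satisfy the entry criteria as a screen failure. It limits their data to demographics and the reason for failing. It does not say that this applies only to failures found before insertion.

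**The concern.** A device-related event rate describes a device only if its numerator and denominator are the subjects exposed to that device. The plan foresees that some subjects may not get the device they were assigned, then groups every summary by assignment. For effectiveness that is the usual choice. For device-related events it credits one product with the other product's harm.

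The second gap is the denominator. Sections 16.5.3 and 16.6 do not say whose events are counted. A subject who had a PICC placed and was later found ineligible is outside the FAS, and the only handling stated for non-FAS information is a listing. Section 10.6, read literally, could go further and stop data collection for that subject. The study is unblinded (section 12.2), so an unspecified denominator could also be settled after the events by device are known.

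At stake are the AE rates and Fisher comparisons by device, which are the plan's safety summary.

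**Working it through.** **1. Which rule reaches the safety tables?** Section 16.1 speaks of all summaries. Section 16.6 says by treatment group, and section 16.5.3 says HydroPICC group against control group. Neither redefines group, so the randomized-arm rule is the only one available. Section 16.3 recognises receipt of the other device but uses it only to remove subjects from the per-protocol set. A subject randomized to device A who received device B therefore appears under A in the 16.6 tables, and a device-related event goes with them.

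**2. Inputs.** Section 10.7 gives 10 analysed and 12 recruited per arm. The plan's own total reproduces: 2 × 10 + 4 = 24 = 2 × 12. Section 16.1 sets a two-sided significance level of 0.05. The documents give no AE or failure rates, so all event counts below are assumptions.

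**3. One subject with an event who received the other device.** Let the assigned arm have h events in n subjects and the other arm c events in n. Regrouping by device received gives:

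- assigned arm: h/n becomes (h − 1)/(n − 1), a fall of (n − h)/[n(n − 1)]. This is largest at h = 1, where it equals 1/n: 10.0 points at n = 10, 8.3 points at n = 12.
- arm of the device received: c/n becomes (c + 1)/(n + 1), a rise of (n − c)/[n(n + 1)]. At c = 0 this is 1/11 = 9.1 points or 1/13 = 7.7 points. At c = 4 it is 6/110 = 5.5 points (n = 10) or 8/156 = 5.1 points (n = 12).

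With h = 1, c = 4 and n = 10, the gap between arms is 40.0 − 10.0 = 30.0 points as randomized and 45.5 − 0 = 45.5 points by device received.

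**4. One treated but ineligible subject with an event, left out.** Restoring the subject turns h/n into (h + 1)/(n + 1). From h = 0 this is 0 to 1/11 = 9.1 points, or 0 to 1/13 = 7.7 points.

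**5. Effect on the planned test.** Two-sided Fisher's exact test, HydroPICC first, comparator second, counts assumed:

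| Case | Randomized arm, or subject left out | Device received, or subject included |
|---|---|---|
| HydroPICC assigned, comparator received, 10 per arm | 1/10 v 4/10, p = 0.303 | 0/9 v 5/11, p = 0.038 |
| Same, 12 per arm | 1/12 v 4/12, p = 0.317 | 0/11 v 5/13, p = 0.041 |
| Ineligible HydroPICC subject with event, 10 per arm | 0/10 v 5/10, p = 0.033 | 1/11 v 5/10, p = 0.064 |
| Same, 12 per arm | 0/12 v 5/12, p = 0.037 | 1/13 v 5/12, p = 0.073 |

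These counts were picked to show that one subject can move a result across 0.05 in either direction. They are not forecasts. A deviation in the opposite direction would shift the rates the other way.

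**The case against.** The best defence is that this is a small pilot of two cleared devices, not powered (section 8) and not intended to support claims (section 16.1). No crossover is planned: section 14.2 has the device inserted as assigned, so receipt of the other device would be a deviation and probably rare. Eligibility is checked by ultrasound before insertion (sections 10.5 and 14.2), which should make treated-but-ineligible subjects uncommon. The safety record is not lost: section 16.6 lists every AE and narrates every SAE, and section 15.2 requires product details for each adverse device effect, serious adverse device effect and device deficiency. Section 16.1 also asks for the denominator of each summary, so an exclusion could be noticed. All of this stands, and it limits the harm to summary rates and tests. It does not change the grouping rule or supply the missing population.

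Three stronger readings are tempting, and the documents do not support them.

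- *The safety tables are restricted to the FAS.* Section 16.3 ties the FAS to the primary analysis only. For sections 16.5.3 and 16.6 the population is unstated, so loss of ineligible subjects is a possible reading, not a stated rule.
- *Failed insertions vanish, so a device with more of them would look best.* Section 10.7 does say "A subject is considered enrolled when the assigned PICC is inserted", but the FAS requires neither enrollment nor insertion: an eligible randomized subject with a failed insertion belongs to it. The other endpoints are blacked out, so whether a failed insertion counts as a failure cannot be seen.
- *Each arm always moves by 8 to 10 points.* The denominators change too. The rise from 4/10 to 5/11 is only 5.5 points.

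**Conclusion.** The point holds in a limited form. Misattribution follows directly from sections 16.1 and 16.6 whenever a subject receives the non-assigned device, a case that section 16.3 itself foresees. The omission of treated-but-ineligible subjects is a reasonable reading of sections 16.3 and 10.6 that the plan should rule out.

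The size is at most about 8 to 10 percentage points in an arm per affected subject, and less where the denominator grows or other events are already present. This assumes 10 to 12 subjects per arm and at least one such subject with an event; the documents give no basis for how likely that is. Whether a Fisher result changes depends on counts that the documents do not supply. The change should be made before the analysis, but the issue does not touch the primary endpoint or the feasibility aim in section 16.2.

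**What to change.** 1. In section 16.3, add a Safety Set: all subjects in whom insertion of a study PICC was attempted, regardless of any later finding of ineligibility, analysed by the device actually placed, or by the device attempted if none was placed.
2. In section 16.6, and for the safety endpoints in section 16.5.3, name the Safety Set as the population and the device placed or attempted as the grouping.
3. In section 16.1, limit the randomized-group rule to effectiveness and baseline summaries.
4. In section 10.6, limit the restriction on data to screen failures identified before insertion.

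No rule is proposed for what counts as a failure endpoint, since those definitions are blacked out.

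The cost is wording. Sample size and significance level are unchanged. Section 15.2 already starts AE collection at the procedure and records the product for device-related events. The device placed or attempted must also be on record for subjects without an event; the surgical summary at Visit 2 is a natural place, though its contents are not shown in the documents. Item 4 means keeping the safety data of any subject found ineligible after insertion.

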16.2. Sample Size Justification

This is a pilot study to see if the ultrasound endpoint is feasible for a larger study. No power analysis was conducted for this study.

16.3. Analysis Populations

The primary analysis will be based on a Full Analysis Set (FAS) analysis population defined as those who were randomized and met all inclusion and exclusion criteria. A Per-Protocol (PP) population will be completed that excludes subjects who have one or more major protocol deviations. Major protocol deviations will be identified prior to locking the database for the final analysis and will include, but are not limited to, not receiving the randomized treatment, not completing the study, and not have met all inclusion and exclusion criteria. Information for subjects not in the FAS population will be listed if available.

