10.4. Exclusion Criteria

- 1) Is pregnant, lactating, or is planning to become pregnant during the time of the study
- 2) Has been previously enrolled in this post market clinical evaluation, or is participating in another clinical study that is contraindicative to the treatment or outcomes of this investigation
- 3) Venous thrombosis in any portion of the vein to be catheterized
- 4) Conditions that impede venous return from the extremity such as paralysis or lymphedema after mastectomy
- 5) Orthopedic or neurological conditions affecting the extremity
- 6) Anticipation or presence of dialysis grafts or other intraluminal devices, including pacemakers, within a month of patient enrollment start
- 7) Patients who are on anticoagulation therapy prior to the study (10-14 days). *Note: (If patients are placed on anticoagulation (low dose) therapy while hospitalized, these patients are allowed.)*
- 8) Patient has relinquished control of care to a guardian and/or facility
- 9) Patient has any significant medical or physical condition that, in the opinion of the PI, would make the subject unsuitable for participation in the post market clinical evaluation
- 10) Inability to complete the protocol in the opinion of the clinical staff due to safety or other reasons

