10.5. Randomization

After consent and review of the inclusion/exclusion criteria, the Investigator can assign a randomization prior to baseline ultrasound. If during the ultrasound procedure, the subject meets an exclusion criterion, then this subject will be considered a screen fail.

[figure not shown]

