10.6. Screen Failures

Any subject who signs an informed consent but fails to meet the required entry criteria is considered to be a Screen Failure. Screen Failure subjects will have their demographic information captured in the appropriate CRF with the reason for screen failure specified. No other information will be collected or analyzed. Since this is a pilot study, the analysis will be conducted on 10 subjects on each arm. If a

[figure not shown]
screen failure occurs, the investigator will need to continue to consent, randomize, and enroll until the 10 subjects for each arm is completed. A second set of randomization envelopes will be used for the recruitment of these screen failed subjects.

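### The primary analysis set (16.3) drops randomized subjects judged ineligible, with no time limit and an open assignment, and the per-protocol set drops them too

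*Combined protocol and SAP*

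**What the plan says.** - **Primary set (16.3).** The primary analysis uses a "Full Analysis Set (FAS) analysis population defined as those who were randomized and met all inclusion and exclusion criteria".
- **Per-protocol set (16.3).** "A Per-Protocol (PP) population will be completed that excludes subjects who have one or more major protocol deviations". The deviations named are "not receiving the randomized treatment, not completing the study, and not have met all inclusion and exclusion criteria". They are to be identified before database lock.
- **Everyone else (16.3).** "Information for subjects not in the FAS population will be listed if available". No third efficacy population is defined.
- **Order of events.** Sections 8.1 and 10.5 place consent and review of the criteria before randomization. Section 10.5 then says that "the Investigator can assign a randomization prior to baseline ultrasound", and continues: "If during the ultrasound procedure, the subject meets an exclusion criterion, then this subject will be considered a screen fail". Section 14.1 has randomization as the last step of Visit 1. Section 14.2 has the scan at Visit 2, before insertion.
- **Blinding (12.2).** There is none.
- **Criteria that rest on opinion (10.4).** Exclusion 9 depends on the investigator's view of suitability. Exclusion 10 reads "Inability to complete the protocol in the opinion of the clinical staff due to safety or other reasons".
- **Screen failures (10.6, 12.1).** Demographics and the reason are recorded. Beyond that, "No other information will be collected or analyzed". Randomized screen failures are replaced, using a second set of envelopes. The definition in 10.6 is not restricted to the period before insertion.

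**The concern.** A full analysis set normally protects the comparison that randomization created, and a per-protocol set then shows what happens when deviators are removed. Here both sets remove the same ineligible subjects, so on this point the second is no check on the first.

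That matters because the people who decide eligibility can know the arm. By the plan's own sequence this can be so at the Visit 2 scan. By the wording of 16.3 it could also be so later, because nothing in the FAS definition says when eligibility is fixed. For the per-protocol set the only limit is database lock, by which time open-label outcomes are known. If knowledge of arm or outcome influences who is called ineligible, the primary comparison carries a selection bias that no planned analysis would reveal. With 10 to 12 subjects per arm, a single decision can be visible in the result.

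**Working it through.** **Inputs.** 10 analysed per arm (10.6); 24 recruited, 12 per arm (10.7); Fisher's exact test for any asymptomatic thrombosis (16.5.1); two-sided 0.05 (16.1); reported asymptomatic thrombosis rate of 48% (6.1), used for illustration only. The plan gives no rate of screen failure after randomization, so every exclusion fraction below is an assumption.

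**The plan's own figure.** 2 × 10 + 4 = 24 = 2 × 12, which agrees with 10.7. There is no power figure to reproduce (16.2).

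**Step 1: the definitions side by side.** FAS = randomized and eligible. PP = no major deviation, where ineligibility is a major deviation. A randomized but ineligible subject is therefore in neither set and is at most listed. Removing ineligible subjects from the PP set is redundant if the FAS has already done so, which suggests that the condition belongs in the PP definition alone.

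**Step 2: exclusion at the pre-insertion scan, with replacement.** This is the late exclusion that the plan describes. Let both arms have true risk p = 0.48. In one arm a fraction f is removed after assignment, the removed subjects would have had risk q, and they are replaced by subjects like those kept. Then

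kept risk = (p − f·q)/(1 − f), and bias = kept risk − p.

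| f | q = 48% | q = 70% | q = 100% |
|---|---|---|---|
| 10% | 0 | −2.4 points | −5.8 points |
| 16.7% | 0 | −4.4 points | −10.4 points |
| 25% | 0 | −7.3 points | −17.3 points |

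For example, f = 1/6 and q = 1 give (0.48 − 0.1667)/0.8333 = 0.376, and 0.376 − 0.48 = −0.104. By exact enumeration at 10 per arm, the chance that Fisher's test falsely favours the arm that lost subjects is 0.64% without selection, 2.1% at f = 16.7% with q = 100%, and 4.3% at f = 25% with q = 100%.

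**Step 3: exclusion after insertion.** The wording of 16.3 leaves this open; the plan does not describe it. At 12 per arm, take 6/12 on the comparator and 1/12 on HydroPICC: Fisher p = 0.069. Calling the one HydroPICC event ineligible gives 6/12 v 0/11: p = 0.014.

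This is a selected case. There are 66 tables at 12 per arm in which the lower arm has at least one event and the other arm has more. Dropping one event from the lower arm moves p from above 0.05 to 0.05 or below in 8 of them. The tables are not equally likely, so 8/66 is a count and not a probability.

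**Step 4: effect of one exclusion on an arm's rate,** for an arm with both events and non-events.

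- Largest: the only event is removed. 1/10 → 0/9 is 10 points; 1/12 → 0/11 is 8.3 points.
- Middle: 6/12 → 5/11 is 50.0% − 45.5% = 4.5 points.
- Smallest: a non-event is removed from 1/12. 1/12 → 1/11 is 9.1% − 8.3% = 0.8 points.

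**The case against.** The strongest reply is that the plan is more orderly than the FAS wording suggests. Sections 8.1 and 10.5 put review of the criteria before assignment, and that review covers exclusions 9 and 10. The one check expressly left until later is the ultrasound. It is done before insertion, when no outcome exists, and the subject is replaced. Once a PICC is in place the subject counts as enrolled (10.7), and no section describes turning an inserted subject into a screen failure. Reasons for screen failure are recorded (10.6), a CONSORT flow diagram is planned (9.1), and subjects outside the FAS are listed (16.3). Section 12.1 leaves the detail of assignment to the statistical analysis plan, and figures around 10.5 and 10.6 are not shown, so the moment at which the envelope is opened relative to the scan is not fully visible.

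Most of this stands, and it rules out three stronger readings that a reader might infer:

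- *That the opinion-based exclusions are routinely judged after assignment.* The stated order says otherwise. They matter only if eligibility is reopened later.
- *That the plan intends to remove subjects once their outcome is known.* It does not say so. The gap is that 16.3 sets no time limit and 10.6 is not confined to the period before insertion.
- *That retained subjects are analysed in the wrong group.* Section 16.1 summarizes by randomized arm. What is lost is completeness of the randomized set.

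What the reply does not remove is that the scan-based exclusion may be made with the arm known, and that both analysis sets exclude on eligibility. Listing and a flow diagram make exclusions visible but do not put the subjects into any comparison.

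**Conclusion.** The concern holds as a gap in definition and sequence. No planned comparison keeps a randomized subject who is judged ineligible; the judgement can follow an open assignment at the scan; and 16.3 does not say when it closes.

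The size depends on facts that the plan cannot supply. If exclusions are unrelated to arm and risk, the expected bias is zero. If they are selective, the illustrations above give a bias of 2.4 to 17.3 points, assuming a 48% rate and removal of 10% to 25% of one arm. One exclusion moves an arm's rate by about 1 to 10 points, depending on the counts, and carries p across 0.05 in some tables only. Nothing in the documents shows that selective exclusion is expected.

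The consequence is modest. Sections 8 and 16.2 describe an unpowered pilot that tests whether the ultrasound endpoint is feasible, and 16.1 says that the study is not meant to support claims. Even so, 16.1 and 16.5.1 plan hypothesis tests at 0.05, and the correction is cheap, so it should be made.

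**What to change.** 1. **10.5, 14.1, 14.2 and the Schedule of Activities.** Complete every eligibility check, including the baseline ultrasound already done at Visit 2, before the envelope is opened. This removes the scan-based, arm-aware exclusion at its source.
2. **16.3.** Define the FAS as all randomized subjects in whom insertion of a study PICC was attempted, analysed in the assigned arm whatever is later found about eligibility. Keep the condition of having met all criteria in the per-protocol definition only.
3. **10.6.** Limit the screen-failure data stop to subjects excluded before insertion. List any subject who was randomized but not inserted, by arm and with the reason.

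Step 2 needs step 1. An FAS based on attempted insertion still leaves out randomized screen failures, and that is harmless only if eligibility was settled before anyone knew the arm.

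**Cost.** Changes of wording, and assignment moves to the procedure visit. A few ineligible subjects may stay in the primary analysis and slightly dilute a difference; the per-protocol set would show the result without them, and so become a real check on the FAS. No extra scans or subjects are needed.

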Exclusion Criteria:	
 1) Is pregnant, lactating, or is planning to become pregnant during the time of the study 2) Has been previously enrolled in this post market clinical evaluation, or is participating in another clinical study that is contraindicative to the treatment or outcomes of this investigation 3) Venous thrombosis in any portion of the vein to be catheterized 4) Conditions that impede venous return from the extremity such as paralysis or lymphedema after mastectomy 5) Orthopedic or neurological conditions affecting the extremity 6) Anticipation or presence of dialysis grafts or other intraluminal devices, including pacemakers, within a month of patient enrollment start 7) Patients who are on anticoagulation therapy prior to the study (10-14 days). Note: (If patients are placed on anticoagulation (low dose) therapy while hospitalized, these patients are allowed.) 8) Patient has relinquished control of care to a guardian and/or facility 9) Patient has any significant medical or physical condition that, in the opinion of the PI, would make the subject unsuitable for participation in the post market clinical evaluation 10) Inability to complete the protocol in the opinion of the clinical staff due to safety or other reasons
Study Duration:	
Enrollment is expected to take about 2 months.
 
Data collection completed when Last Subject Last Visit occurs. (Calculated by date of procedure + 12 days for the last subject)

Reported Adverse Event Data:	Product observations and adverse events will be collected and reviewed per
	[REDACTED] (product complaints). Additional safety evaluations will be
	performed if needed.

Schedule of Activities

Subject Timepoints	Visit 1 Screening (- 7 days)*	Visit 2 Procedure (0 day)	Visit 3 7 day evaluation (± 5 days)	Visit 4 14 day evaluation and End of Study (± 7 days)***	Unscheduled visits (as needed)
ICF	X				
Inc/Ex criteria	X				
Medical History	X				
Demographics	X				
Con Meds	X	X	X	X	X
Labs (specific per protocol and standard of care)	X	X	X	X	X
Randomization	X**	X**			
Surgical Summary		X			
Ultrasound (as needed per DVT, AND at these specific timepoints)			X	X	X
AE/SAEs		X	X	X	X
Follow up form/unscheduled visit form			X	X	X
End of study forms				X	

*Screening can happen on the same day of the procedure. Screening can also happen 7 days prior to the procedure.

**Randomization can occur at screening or prior to procedure.

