7.1. Primary Objective and Endpoints

The primary purpose is to examine the incidents of early asymptomatic thrombosis between the HydroPICC arm and the comparison arm.

By using ultrasound technology, the site will measure early incidents of all asymptomatic thrombosis inclusive of superficial thrombophlebitis (SVT) and deep venous thrombosis (DVT). Subjects will be requested to have the PICC line scanned at 7 days (\pm 5 days), and at any unscheduled visit where a symptomatic SVT or DVT is suspected.

The ultrasound evaluation will be classified as (1) without thrombosis or (2) with limited (~2-4mm), (3) large (~4 mm), or (4) occlusive thrombosis, as compared to baseline. Please see the ultrasound section below for more details.

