11.5. Use of Data Following Withdrawal

Data collected while the subject provided will be used for the overall analysis. No data will be collected or analyzed from the date that the subject withdrew from the study.

12. Study Treatment

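### The per-protocol set requires completion through Visit 4 for every endpoint, so a valid day-7 primary scan leaves that set if the subject is lost afterwards

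*Combined protocol and SAP*

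**What the plan says.** - **Per-protocol set (section 16.3).** It "excludes subjects who have one or more major protocol deviations", and the named deviations include "not receiving the randomized treatment, not completing the study". One definition serves all endpoints.
- **Discontinued subjects (section 11).** "Data from the discontinued subject will not be used for the per protocol analysis". Replacement is triggered "If a subject is unable to complete the study for any reason". Neither rule separates losses before the day-7 scan from losses after it.
- **Primary endpoint (section 7.1).** "Subjects will be requested to have the PICC line scanned at 7 days" (± 5 days), plus any unscheduled visit for a suspected symptomatic event. Section 16.5.1 tabulates the primary endpoint no further than the 7-day visit.
- **End of study.** The Schedule of Activities in section 4 heads Visit 4 "14 day evaluation and End of Study" (± 7 days). Section 14.4 places the end-of-study form there, at least 4 days after Visit 3.
- **Primary analysis (section 16.3).** It is based on the Full Analysis Set: randomized subjects who met the entry criteria, with no completion condition.
- **Withdrawals (section 11.5).** "Data collected while the subject provided will be used for the overall analysis".
- **Loss allowance (section 10.7).** The plan is to analyse 10 per arm, but "the site will recruit for 12 in case of COVID related follow up issues".

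**The concern.** A per-protocol exclusion should reflect a deviation that affects the endpoint being analysed. Missing Visit 4 cannot make a scan taken at Visit 3 less valid. Requiring Visit 4 is reasonable for an endpoint that uses the 14-day scan. The difficulty is that the same requirement is applied to the day-7 endpoint.

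Two things follow for the per-protocol analysis of the primary endpoint. Usable scans are left out of a very small trial whose stated purpose (section 16.2) is to learn whether the ultrasound endpoint is feasible. The set is also selected on something that happens after the outcome is known. The trial is unblinded (section 12.2), so staff and subjects may know both the arm and the day-7 result before Visit 4 is missed.

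**Working it through.** **Timing.** Visit 3 may fall on days 7 − 5 = 2 to 7 + 5 = 12. Visit 4 may fall on days 14 − 7 = 7 to 14 + 7 = 21. With the 4-day minimum, the gap between them runs from 4 days to 21 − 2 = 19 days. Under sections 11 and 16.3, a subject lost in that gap leaves the per-protocol set with the primary scan already recorded.

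**The plan's own figure.** 2 × 10 + 4 = 24 enrolled, or 12 per arm. The implied loss is 4/24 = 16.7%, and 20 / (1 − 4/24) = 24. The figure reproduces. There is no power calculation to reproduce.

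**Scans at risk.** The documents do not say when losses would occur. The range is 0 scans (all losses before Visit 3) to 4 of 24 (all after it), or 2 of 12 per arm if evenly split.

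**Precision.** The standard error of a risk difference scales as 1/√n. Going from 12 to 10 per arm multiplies it by √(12/10) = 1.095, about 10% wider. This overstates the cost relative to the plan, because 10 per arm is the intended analysis size and replacement would refill the set.

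**Bias.** Let p be the true day-7 rate, and q+ and q− the chances of being lost after a positive or negative Visit 3 scan. Then

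per-protocol rate = p(1 − q+) / [p(1 − q+) + (1 − p)(1 − q−)]

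Take p = 48.82%, the background figure for cancer patients in section 5.2, which is not a design assumption. All q values are assumptions.

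| q+ | q− | Calculation | Per-protocol rate | Scans lost per 12 |
|---|---|---|---|---|
| 1/6 | 1/6 | 0.4068 / (0.4068 + 0.4265) | 48.8% | 2.0 |
| 1/3 | 0 | 0.3255 / (0.3255 + 0.5118) | 38.9% | 1.95 |
| 1/2 | 0 | 0.2441 / (0.2441 + 0.5118) | 32.3% | 2.93 |

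At an assumed true rate of 24%, the last two rows become 17.4% and 13.6%.

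When q+ = q−, the rate is unchanged. Loss that differs only by arm, with q+ = q− inside each arm, thins one arm but does not shift its expected rate. Bias therefore needs loss related to the scan result, either alike in both arms or differently by arm. The comparison is most exposed if the relation differs by arm.

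**The case against.** **The primary result is protected.** This stands. The Full Analysis Set does not require completion, and section 11.5 keeps data collected before withdrawal for the overall analysis. A reader might infer that day-7 scans are lost to the trial or that the main conclusion changes. The documents support neither: the scans leave the per-protocol set only. What remains unstated is how replacing non-completers and analysing 10 per arm fit with the Full Analysis Set.

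**Per-protocol is not the only supporting analysis.** Also right. Section 16.5.1 adds a Fisher's exact test of any thrombosis and a separate summary of COVID-19 subjects.

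**Completion is not defined.** Section 8.1 ties participation to the time the catheter is in place, up to 16 days. The synopsis computes the last visit as procedure plus 12 days. The Visit 4 window runs to day 21. Section 14.4 lists therapy as an end-of-study reason alongside completion. A reader might infer that a subject whose therapy finishes after Visit 3 is a non-completer, but the text does not settle that. Loss to follow-up is the clear case.

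**Late loss may be rare.** Section 11.1 encourages discontinued subjects to complete the remaining visits, so the full allowance falling after Visit 3 is a worst case. Even so, section 11 excludes discontinued subjects' data without exception.

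**Crossing 0.05.** A reader might build tables in which a late loss changes significance. These depend on who is chosen. From 1/12 v 7/12 (Fisher p = 0.027), one loss per arm can give 1/11 v 6/11 (p = 0.063) or 1/11 v 7/11 (p = 0.024). That is small-sample instability, not evidence of bias.

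**Unscheduled scans.** Section 7.1 also counts these, so a loss before Visit 4 can shorten the period in which one might occur. It does not undo the scheduled scan.

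**Conclusion.** The point holds for the per-protocol set and is minor. The completion rule is tied to Visit 4 for an endpoint read at Visit 3, so a subject lost in between is excluded, and replaced, after supplying a valid primary scan. At most 4 of 24 scans leave the set if the whole loss allowance falls after Visit 3.

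Loss unrelated to the scan costs precision only. Result-related loss is possible in an open-label trial, and the 48.8% to 38.9% shift shows what it could do, but it rests on assumed loss rates. The documents contain no evidence that such loss will occur. The study is also an unpowered pilot that section 16.1 says is not meant to support claims.

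**What to change.** **Section 16.3.** Replace study completion as a deviation with an endpoint-specific rule: no evaluable Visit 3 scan for the primary endpoint, and no evaluable Visit 4 scan for endpoints that use the 14-day scan. Define completing the study, and reconcile that definition with the participation period in section 8.1, the last-visit calculation in the synopsis and the Visit 4 window.

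**Section 11.** State that data measured before discontinuation stay in the per-protocol analysis of the endpoint they belong to, and that a subject with a Visit 3 scan is not replaced for the primary endpoint.

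**Cost.** Wording in two sections, with no new data or visits. The per-protocol denominators will differ between the day-7 and day-14 tables. Section 16.1 already asks for the denominator with each summary, so the difference will be visible.
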